5. TREATMENT OF SUBJECTS

Not applicable

6. INVESTIGATIONAL PRODUCT

Not applicable

7. NON-INVESTIGATIONAL PRODUCT

Not applicable

8. METHODS

8.1 Study parameters/endpoints

8.1.1 Main study parameter/endpoint

The primary endpoint of this study is the identification of genetic variant(s) in an affected patient and establishment that this/these genetic alteration(s) is/are (likely) pathogenic (with a deleterious impact on protein function; ACMG class IV or V) and causal of disease.

8.1.2 Secondary study parameters/endpoints

Identification of phenotypic presentation/ disease characteristics to facilitate recognition of disorders in other undiagnosed patients

8.1.3 Other study parameters

[figure not shown]
Evaluation of the yield of the diagnostic approach used in the study. Yield of integrated analysis of the –omics datasets and whole exome/whole genome sequencing dataset for validation of causality of the identified variants.

8.2 Randomisation, blinding and treatment allocation

Not applicable

8.3 Study procedures

See Figure 1, pag24

pigmentosa (RP)), endocrine (hypoparathyroidism, hypoglycemia)

Intoxication: neurological (encephalopathy, regression, movement disorder, psychiatric symptoms), ophthalmological (lens luxation), organic (liver and kidney function abnormalities)

Storage: neurological (regression, psychiatric symptoms), ophthalmological (cataract/corneal clouding), organic (hepatosplenomegaly, cardiac hypertrophy, skeletal abnormalities, short stature, coarse facial features, umbilical/inguinal hernia)

² abnormal: metabolites in body fluids (CSF, urine, blood)/ Functional studies at a biochemical/ cellular level/radiological (neuro)imaging suggesting a deficient metabolic pathway or process and/or a VUS (variant of unknown significance) in a gene involved in metabolism

* adult/pediatric metabolic physician, neurologist, psychiatrist, clinical geneticist

Patient referral

Patients with an unexplained metabolic phenotype are eligible for inclusion in the study (see inclusion criteria 4.2, pages 19-20) *only* once all ‘standard of care’ clinical diagnostic tests have proved inconclusive (see inclusion criteria 4.2, pages 19-20). Thus, no clinical diagnostic procedures will be postponed because of participating in the study.

The treating physician will ask the patient for consent to share his/her data with the multidisciplinary clinical meeting of the ZOEMBA team. After patient consent, the referring specialist will make a patient resume, using a standard format, which will be used for discussion at the multidisciplinary patient meeting the “ZOEMBA-team triage meeting” (1x per 2-4 weeks).

The ZOEMBA team for this meeting exists of:

- Study coordinators: Dr. [name] (Study PI, Pediatrician in Inborn errors of metabolism & Biochemical Geneticist– Amsterdam UMC), Dr [name] (internal medicine specialized in IEM), Prof [name] (Study CoPI, head of the Laboratory of Metabolic Diagnostics, UMC Utrecht), Dr. [name] (coordinating postdoctoral fellow, clinical geneticist specialized in IEM, Amsterdam UMC)
- A clinical and laboratory representative per participating UMC (when not already represented by the study coordinators):
 - Amsterdam UMC: Prof. dr. [name] (PI at the laboratory of GMD), Dr [name] (Clinical Chemist IEM, Laboratory GMD, specialized in lipidomics)
 - UMCU: Dr. [name] (Pediatrician in IEM) and Dr. [name] (laboratory specialist, Laboratory of Metabolic Diagnostics, specialized in metabolomics)
 - UMCG: Prof. dr. [name] (Pediatrician in IEM), Dr. [name] (Clinical Chemist IEM, Laboratory of Metabolic Diseases, specialized in IEM)
 - MUMC: Prof. dr. [name] (Pediatrician in IEM), Dr. [name] (Clinical Chemist IEM, Laboratory for GMD)
 - Radboudumc: Dr. [name] (Internist in IEM), Dr. [name] (Clinical Chemist IEM, Translational Metabolic Laboratory)
 - Erasmus UMC: Dr. [name] (Pediatrician in IEM), Dr. [name], Clinical Chemist, Laboratory for Inherited and Metabolic Diseases)
- The referring medical specialist

Patient journey: exclusion or inclusion

In case of exclusion (see page 21) the patient and referring specialist will receive a letter of exclusion within 2 weeks after ZOEMBA-team triage meeting.

When meeting inclusion criteria, patients will receive an invitation for an appointment with the MD-PhD student at the outpatient clinic. During the visit the patient will receive information about the study. When patients have understood the procedure, informed consent (1) will be asked for within 24 hours.

During the whole of the study, appointments will be combined with regular hospital visits if possible.

Informed consent

Retrieving data from the patient's medical records

Medical data including medical and social history (developmental milestones, level of education, neuropsychological testing), family history, and physical and neurologic examination

Diagnostic/laboratory data including cerebral MRI-scan, skeletal X-rays, ECG.

In case of specific dysmorphic features the patient has an option to consent for the use of medical photographs for teaching goals and/or for publication. Specific dysmorphic features can be essential for establishing a quick clinical diagnosis and can lead to significant shortening the diagnostic trajectory.

All relevant patient data are documented pseudo-anonymized in standardized data collection forms (synonym: Case Report Form, CRF).

Safeguarding previous (stored) samples

Neonatal dried blood spot card (to be requested from RIVM)

Plasma samples

Urine samples

CSF

Skin fibroblasts, muscle biopsy, chorionic villi

Amniotic fluid.

Data sharing (pseudo-anonymized) through RD-Connect

- 1) For identification of additional patients with a VUS in the same gene
- 2) To share knowledge according to FAIR principles. Data will be shared pseudo-anonymized through this international database

Sampling blood and urine

Of all patients, blood and urine will be collected

Blood:

Adults: 50 ml in heparinized tubes for metabolomics and 0,5 ml in EDTA tube for lipidomics (total of 50,5 ml)

Children: 10 ml in heparinized tubes for metabolomics and 0.5 ml in EDTA tube for lipidomics (total of 10,5 ml)

Children <2 years of age: assessed on a case-by-case basis (prioritization of investigation)

From the heparinized blood, 3 dried blood spots (DBS) will be made. Samples will be treated and stored as described in a standardized protocol.

Urine: of all ages a minimum from 4- 10 ml will be collected.

Sampling from family members

Blood samples of unaffected parents and/or siblings will be asked for to store DNA. Sample collection for DNA isolation consists of:

In adults: 10 ml blood in EDTA tubes.

In children: 2 ml blood in EDTA tubes.

Of unaffected family members (parents and/or siblings) informed consent will be asked to use previously collected DNA samples. In case no (not enough) DNA is available consent is asked for collection of new blood samples for storage of DNA. For the reanalysis of WES-data and WGS, DNA of these family members will be used as reference. In case a candidate variant is identified, DNA of unaffected family members will be used to test *inheritance pattern of his variant only* (in **Step I**). No other tests will be run on the DNA from the unaffected family members.

In case of similarly affected family member, this patient can be included, after informed consent. He/she will be treated similar to the index patient.

Diagnostic Step I

- Reanalysis previous WES-data

The bioinformatic pipeline will be optimized to detect pathogenic variants. The bioinformatician will generate a variant list with potential pathogenicity determined by comparison to existing databases such as ClinVar, Exac or HGMD. After use of *in silico* predictors and consideration of conservation and minor allele frequencies, potentially pathogenic variants will be reported for discussion within the StU-team.

- Samples

The blood samples will be processed within 1 hour after sampling. DBS will be made, after which the samples are centrifuged, aliquoted and stored at the Amsterdam UMC at -80 °C. Urine samples will be stored at -80 °C.

- WGS

WGS will be performed with a minimum coverage of 45x for the patient and 30x for the parents. Raw data will be provided as fastq files and variant calls will be provided as BAM files and vcf files. The analysis will be run, like WES, as trios whenever possible. In case the parents of a patient are not available for research, DNA of other preferably affected siblings

or unaffected family members will be used instead, only after consent. DNA will be directly transferred to the Radboudumc in Nijmegen for the distribution of the material to an external party. WGS data will be generated by BGI Genomics, a commercial international genome sequencing facility located in Shenzhen, China. BGI Genomics is the world's leading provider of genomic sequencing services and proteomic services, now serving customers in more than 66 countries. They provide academic institutions, pharmaceutical companies, health care providers and other organizations with integrated genomic sequencing and proteomic services and solutions across a broad range of applications spanning. They have almost 20 years of genomics experience helping customers achieve their research goals by delivering rapid, high quality results using a broad array of cost-effective, cutting-edge technologies, including innovative DNBseq™ sequencing technology. The generated WGS data is thereafter transferred to our ZOEMBA bioinformatics specialist in the Radboudumc. Here the WGS data is analyzed and interpreted in order to find a diagnosis. No data or (surplus) material will be stored by BGI genomics and will be destroyed shortly after data transferal.

The Radboudumc has signed a contract with this third party, regarding material ownership, confidentiality and destruction of sample after use. We highlight the following clauses, which address the aforementioned topics:

1.1 BGI Genomics shall deliver data to Radboudumc no later than 60 days following the completion of services related to the Data delivered under the agreement. Data will be shipped to Radboudumc as generated

1.2 Data delivered to Radboudumc shall be deleted by BGI Genomics no sooner than 30 days after data delivery of the data to Radboudumc as provided in 1.1 unless otherwise specified in writing by the parties, and will be destroyed in accordance with all applicable laws.

1.3 Samples from Radboudumc will be sequenced for the studies by BGI Genomics may provide additional samples in the context of these clinical utility studies with the prior written consent hereto from Radboudumc. Data analysis will be performed by Radboudumc scientists, but if desired by Radboudumc, collaboration with BGI Genomics scientist can take place and will be made possible by BGI Genomics.

1.4 Upon delivery, Radboudumc shall own all rights to the Data. Under no circumstances shall BGI Genomics have any ownership interest in the Data.

- Metabolomics

The coded and anonymized DBS will be transported to the section Metabolic Diagnostics of the UMC Utrecht and plasma samples (1ml) will be shipped to Radboudumc for metabolomics in DBS and plasma respectively. Packing, shipping, and tracking of samples will be coordinated by the research coordinator.

Patients will have a telephone appointment with the arts-onderzoeker within 6 months to discuss the first results of the reanalysis of the WES-data and of the metabolomics. The arts-onderzoeker will explain further diagnostic trajectory and expected timeline.

Potential outcomes of Diagnostic step 1 (see Figure 1)

1. Known genetic diagnosis

Patients will be invited for an appointment with the arts-onderzoeker and one of the MD's from the StU team at the outpatient clinic to discuss the findings. Hereafter, patients and their referring physicians will receive a letter explaining the diagnosis and confirming the exit of the study. Follow up/treatment of the patient will be organized by the referring physician.

2. No genetic diagnosis

The following additional tests will be performed (**Step IIB, see Figure 1**)

- *Deep WES (200+X) (performed on previously collected DNA)*

For deep WES the bioinformatic pipeline will be optimized to detect pathogenic variants (as has been described under Diagnostic step 1). Deep WES data will be generated by the involved UMC's.

- *(and/or) Lipidomics/Glycomics on previously collected blood samples in Step I.*

Lipidomics will be performed in EDTA plasma (50 µl) at the Amsterdam UMC, location AMC. Analysis of plasma protein glycosylation will be performed in heparinized plasma (<50 µl) at the Radboudumc Nijmegen.

Patients will have a telephone appointment with the arts-onderzoeker within 6 months to discuss the results of these tests.

In case a candidate genetic variant is found, patients will go to **3 (Step IIA), see below**.

In case the cause for the patient's phenotype still remains unclear, possibility of a future diagnosis and recontact still remains possible if other patients have been identified via data-sharing (see **underneath 3 (Step IIA)**).

3. Candidate genetic variant (Step IIA, see Figure 1)

When either direct after diagnostic Step 1 or via Step IIB, a candidate gene has been identified, patients will be invited for an appointment with the arts-onderzoeker at the outpatient clinic for explanation of the finding and further plans.

Additional samples will be collected and additional tests will be performed: repeat metabolomics (blood and urine; similar to **Step I**), RNA-analysis and skin biopsy for fibroblasts (in case no previous sample is available)). These tests are needed to further study causality of the identified genetic variant.

Sampling blood and urine

Of all patients, blood and urine will be collected

Blood

Adults: 50 ml in heparinized tube for repeat and additional metabolomics

and 20 ml in PAX tubes for transcriptomics (a total of 70 ml of blood will be drawn)

Children: 10 ml in heparinized tubes for repeat and additional metabolomics and 3 ml blood in PAX tubes for transcriptomics (total of 13 ml)

Children <2 years of age: assessed on a case-by-case basis (prioritization of investigation)

From the heparinized blood in the tube, 3 dried blood spots (DBS) will be made. Samples will be treated and stored as described in a standardized protocol.

Urine: of all ages a 4-10 ml will be collected.

Skin biopsy

When no previous fibroblasts are available, additional consent will be asked to perform a skin biopsy. Skin biopsies will be taken according to standard clinical procedures.

In case the patient will receive anesthesia for a planned procedure (not study-related), a skin biopsy will be combined with this procedure if possible.

After collecting the additional samples, the following will be pursued to further validate causality in **Step IIA**:

- *Datasharing* via RD-Connect (for MatchMaker Exchange)
- *DNA segregation analysis* of the identified candidate genetic variant in unaffected family members will be performed to establish correlation between variant and phenotype.
- *Lipidomics* (in case lipid metabolism is suspected to be affected) is performed in EDTA plasma (50 µl) at the Amsterdam UMC, location AMC.
- *RNA sequencing* will be performed in the collected blood samples and/or fibroblasts.
- For *functional studies*, fibroblast cell cultures, derived from the patient's skin biopsy, will be used. These studies will be performed by the associated research groups of prof. dr. [name], dr. [name], dr. [name] (Amsterdam UMC, location AMC), dr. [name], dr. [name] and prof. [name] (UMC Utrecht) and dr. [name] (Radboudumc).

Depending on the type and number of additional tests, the generation and interpretation of these final results may take from 3 months up to 1 year. Therefore, patients and the referring

specialists will receive an update every 6 months by letter to inform them on the latest results.

When results correlate with the patient's phenotype and a diagnosis can be made, the patient will follow point 1 and will be invited for an appointment with the 'arts-onderzoeker' and the MD involved at the outpatient clinic to discuss the findings.

When, with additional testing, the causality between the genetic variant and the patient's phenotype still remains unclear, unraveling the genetic cause still remains possible by identifying another (phenotypical/metabolic/genetic) similar patient through the database of RD-connect. In case new information becomes available leading to a possible diagnosis during, patients will be recontacted by the arts-onderzoeker.

Research meetings on patient data

To discuss the results of data collected from Step I, Step IIA and Step IIB and to establish a validation plan, a biweekly research meeting, called the ZOEMBA diagnostic meeting will be organized. The referring medical specialist and involved lab scientists will be invited to attend the meeting. The meeting will be conducted by the participants of the ZOEMBA team below and will be organized via teleconference.

The ZOEMBA team for this meeting exists of:

- Study coordinators: Dr [name] (Study PI, biochemical geneticist and pediatrician specialized in IEM, Amsterdam UMC), Prof. dr. [name] (Study CoPI, head of the laboratory of GMD, UMC Utrecht), Dr. [name] (coordinating postdoctoral fellow, clinical geneticist specialized in IEM, Amsterdam UMC)
- Omics datasets: Dr [name] (lipidomics, Amsterdam UMC), Dr [name] (metabolomics Radboudumc), Dr [name] (metabolomics, UMC Utrecht), Prof [name] (glycomics, Radboud UMC)
- Functional metabolic assays: [name]. [name] and dr. [name] (Amsterdam UMC), Dr [name] (Radboudumc)

8.4 Withdrawal of individual subjects

Capacitated patients can leave the study at any time for any reason if they wish to do so without any consequences. The investigator can decide to withdraw a patient from the study for urgent medical reasons.

In case of incapacitated subjects (children or patients with an ID) any sign or behaviour (verbal or non-verbal) that can be interpreted as resistance will be taken into account and discussed with the caregivers and family. When consistent and seen as resistance this will lead to immediate withdrawal of the study (gedragscode verzet minderjarige en gedragscode verzet verstandelijk gehandicapt, NVK).

In case of withdrawal all data will be removed from the study file and biological samples of the patients will be destroyed. Data uploaded at RD-Connect will either stay there or be removed depending on the patients or the legal guardians wishes .

8.4.1 Specific criteria for withdrawal (if applicable)

Not applicable

8.5 Replacement of individual subjects after withdrawal

Because this study is about RD and single patient diagnosis, we will as such not replace individuals after withdrawal.

8.6 Follow-up of subjects withdrawn from treatment

Patients who withdraw from the study will follow their regular care (no specific study follow-up).

8.7 Premature termination of the study

Premature termination of our study will follow in the highly unlikely case that no patients will be included.

9. SAFETY REPORTING

9.1 Temporary halt for reasons of subject safety

In accordance to section 10, subsection 4, of the WMO, the sponsor will suspend the study if there is sufficient ground to assume that continuation of the study will jeopardise patient's health or safety. The sponsor will notify the accredited METC without undue delay of a temporary halt including the reason for such an action. The study will be suspended pending a further positive decision by the accredited METC. The investigator will take care that all subjects are kept informed

9.2 AEs, SAEs and SUSARs

9.2.1 Adverse events (AEs)

Adverse events are defined as any undesirable experience occurring to a subject during the study. All adverse events reported spontaneously by the subject or observed by the investigator or his staff will be recorded.

The only invasive procedures undertaken in this study are vena puncture and skin biopsy. We do not expect any adverse events from this procedure, but in case of occurrence they will be reported to the accredited METC.

9.2.2. Serious adverse events (SAEs)

Not applicable since non-interventional study and study procedures (vena puncture/skin biopsy) cannot lead to a serious adverse event.

9.2.3 Suspected unexpected serious adverse reactions (SUSARs)

Not applicable

9.3 Annual safety report

Not applicable

9.4 Follow-up of adverse events

All AEs will be followed until they have abated, or until a stable situation has been reached. Depending on the event, follow up may require additional tests or medical procedures as indicated, and/or referral to the general physician or a medical specialist.

SAEs need to be reported till end of study within the Netherlands, as defined in the protocol

9.5 Data Safety Monitoring Board (DSMB)

Our study does not require the installation of a DSMB. Nonetheless, we plan to perform a mid-term evaluation after one year to evaluate the inclusion progress: in case the rate is lower than expected we will try to identify causal factors. The mid-term analysis will be performed by the ZOEMBA team.

10. STATISTICAL ANALYSIS

The only statistics will be a descriptive analysis on the number of patients included. We will also report the number of patients with a confirmed diagnosis and the average time to diagnosis.

10.1

Not applicable

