3. STUDY DESIGN

This is a national multicenter prospective diagnostic study. The study is expected to run for at least 5 years.

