4. STUDY POPULATION

4.1 Population

A total of 500 (in)capacitated patients (any age/gender) will be included, with an unexplained metabolic phenotype (see inclusion criteria), in whom no conclusive diagnosis has been established after extensive 'standard of care' clinical work-up (see inclusion criteria). Patients will be referred from the outpatient clinics of all participating university medical centres in the Netherlands: paediatrics, internal medicine, neurology, clinical genetics and psychiatry.

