4.4 Sample size calculation

A previous study in 47 (predominantly pediatric) patients with unexplained ID plus metabolic phenotypes (executed by the principal and coordinating investigator of the current study) showed a high diagnostic and discovery yield using an integrated approach with deep phenotyping, WES and metabolomics followed by functional analyses; a diagnosis was established in 68% of all patients plus a novel human disease gene identified in 11 patients. 44% of these diagnoses were amenable to causal therapies, including specific dietary restriction, supplementation or pharmacologic interventions.

In the proposed study, which focuses on unsolved cases after standard diagnostic trajectories and with inclusion of adults with more diverse phenotypes, we expect the yield to be lower. We make a conservative estimate of a diagnostic yield of 33% (comparable to findings from the NIH Undiagnosed Diseases Program of 34% (Gahl et al., 2016; Splinter et al., 2018)), and an expected discovery rate of a novel candidate gene 1 in 25.

Thus, we estimate to diagnose 170 patients, including 20 with novel candidate disease genes. With an inclusion period of at least 5 years, we expect to enrol on average 100 patients per year. The number of patients referred and / or enrolled per year will likely differ per UMC based on expertise and focus. A recent investigative query among the 6 UMCs has shown that our aim of enrolling 500 undiagnosed patients suspected to have an IEM is realistic based on their annual patient numbers and diagnostic trajectories.

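### The planned average time to diagnosis can be computed only in the roughly one third of patients who are diagnosed, so it is not a valid summary of time to diagnosis in the cohort

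*Protocol*

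**What the plan says.** Section 10 limits the analysis to description: "The only statistics will be a descriptive analysis on the number of patients included". It then adds: "We will also report the number of patients with a confirmed diagnosis and the average time to diagnosis". It gives no time origin, does not say which patients enter the average, and has no rule for patients still undiagnosed at the end. Sections 10.2, 10.3 and 10.5 are marked as not applicable.

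The other relevant statements in the protocol are these:

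- **Size and yield (sections 4.1 and 4.4):** "A total of 500 (in)capacitated patients (any age/gender) will be included"; "We make a conservative estimate of a diagnostic yield of 33" per cent; "Thus, we estimate to diagnose 170 patients, including 20 with novel candidate disease genes".
- **Entry and duration (sections 4.4 and 3):** "With an inclusion period of at least 5 years, we expect to enrol on average 100 patients per year"; "The study is expected to run for at least 5 years". The two minimum lengths are the same.
- **Order of work-up (section 8.3):** first results of exome reanalysis and metabolomics are discussed within 6 months. Step IIB results follow within 6 months. For Step IIA, "the generation and interpretation of these final results may take from 3 months up to 1 year". Matching with other patients is open-ended.
- **Closure (section 12.5):** the wording is unclear, but the study can end when the study period lapses.
- **Withdrawal (section 8.4):** all data of a withdrawn patient are removed from the study file.

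**The concern.** A patient who is never diagnosed has no time to diagnosis. At the expected yield, about two thirds of the cohort cannot enter an ordinary mean. Two features of the design then act on the mean of the remaining third.

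First, diagnoses from later steps come later. Each additional difficult case solved raises the mean, although no other patient waits longer.

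Second, if closure follows soon after the last enrolment, late diagnoses in late entrants are not observed. That lowers the mean. The two effects run in opposite directions, so a reader cannot tell what a given value reflects.

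This is the only time figure in section 10, and the introduction stresses how long diagnostic trajectories last. Readers are likely to take it as the time that a participant can expect to wait, which it does not measure.

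**Working it through.** **The plan's own figures.** 500 × 0.33 = 165, against the stated 170. The stated figure matches 500 × 0.34 = 170, using the 34% of the comparison programme cited in section 4.4. 500 / 25 = 20 novel candidate genes and 5 × 100 = 500 patients both agree. The average thus rests on 165 to 170 patients, and 330 to 335 contribute nothing. The protocol states no expected time to diagnosis, so there is no time figure to reproduce.

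**Time paths implied by section 8.3.** If each interval given as within 6 months takes the full 6 months:

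- Step I then IIA: 6 + 3 = 9 to 6 + 12 = 18 months.
- Step I, IIB, then IIA: 6 + 6 + 3 = 15 to 6 + 6 + 12 = 24 months.

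At 100 patients per year, about 200 enrol in the last 24 months of a 60-month inclusion period. If the study closed at month 60, these patients might not complete the longest path.

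**Effect of closure, with three fixed times.** The timings and shares are assumptions: among solved patients, 50% are diagnosed at 6 months, 30% at 15 and 20% at 30. Entry is uniform over 60 months.

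- True mean: 0.5 × 6 + 0.3 × 15 + 0.2 × 30 = 13.5 months.
- Closure at month 60: the chances of being observed are 54/60, 45/60 and 30/60, giving weights 0.45, 0.225 and 0.10.
- Reported mean: (0.45 × 6 + 0.225 × 15 + 0.10 × 30) / 0.775 = 9.075 / 0.775 = 11.7 months, which is 13% short.
- Longest time capped at 24 months: true mean 0.5 × 6 + 0.3 × 15 + 0.2 × 24 = 12.3. The weights are 0.45, 0.225 and 0.12, so the reported mean is 8.955 / 0.795 = 11.3, which is 8% short.
- Closure at month 84 instead: with the 24-month cap every diagnosis is observed and the bias is zero. With 30 months the third weight is 0.2 × 54/60 = 0.18, and the mean is 12.9 / 0.98 = 13.2, about 2% to 3% short.

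**Sensitivity, with exponential times.** These are simulated with 33% solvable, uniform 5-year entry and closure at year 5. A true mean of 6 months is observed as about 5.3, 12 as about 9.1, 18 as about 11.6 and 24 as about 13.2. A mixture of 20% easier cases (mean 6 months) and 13% harder ones (mean 18) has a true mean of 10.7. It is observed as about 7.5, or about 9.2 with two further years of follow-up.

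**Effect of solving harder cases, without closure.** Take 20% of patients solved at mean 6 months and add h% solved at mean 18 months. The mean is (20 × 6 + h × 18) / (20 + h): 6.0 for h = 0, 8.4 for h = 5, 10.7 for h = 13 and 12.0 for h = 20.

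**Mean against cumulative incidence.** These two programmes are assumed, with exponential times. Cumulative incidence is the sum of share × (1 − exp(−t/mean)).

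- Programme 1 solves 20% at mean 7.2 months: 16.2% diagnosed by 12 months and 19.3% by 24. The mean among solved is 7.2.
- Programme 2 solves the same 20% faster (mean 6) and a further 13% at mean 18: 23.6% by 12 months and 29.2% by 24. The mean among solved is 10.7.

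The mean among solved patients ranks Programme 2 as slower, although it has diagnosed more patients at both time points.

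**The case against.** The strongest reply is that the figure is descriptive and carries no claim. Sections 2 and 8.1 do not make speed an objective or endpoint, and the comparative aim in the introduction is yield. A mean among diagnosed patients legitimately describes how long those patients waited. The number diagnosed is reported in the same sentence, so a programme that looked quick because it solved few patients would be visible. Origin and censoring rules could stand in an analysis plan that is not shown. The inputs to the illustration are also not the protocol's: nothing gives 30 months, the 6-month call does not cover genome sequencing, and closure at month 60 is the least favourable case because both periods are minimums.

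Most of this stands, and it limits the point in three ways.

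- A reader might infer that the protocol defines the average for solved patients only. It does not define the average at all. The restriction follows from the arithmetic of a mean at 33% yield.
- A reader might infer that the figure is meant to show faster diagnosis and fails to. The protocol never states that use, and without a comparator for time no summary from this study could show it alone.
- The size of the closure effect is unknown. It is small if most diagnoses come within about 6 months or if follow-up is extended.

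The choice of summary remains open to criticism. Section 10 calls its contents the only statistics and names an average. Reporting the count beside it does not remove the effect of closure, which lowers the observed count as well.

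**Conclusion.** The point holds for a descriptive figure. As named in section 10, the average can describe only the patients who are diagnosed before closure. It is not a valid summary of time to diagnosis among those enrolled.

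Both directions of distortion follow from the design if later-step diagnoses take longer and closure comes before late entrants are worked up. The first condition is supported by section 8.3. The second is possible under sections 3, 4.4 and 12.5 but not certain.

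With closure at month 60, the shortening is 8% to 13% under the fixed-time illustrations. Under the exponential ones it ranges from about 0.7 months on a true mean of 6 to about 3.2 months on 10.7 in the mixed case, and is larger still if times are longer. All these timings are assumptions. No result on yield is affected by the choice of time summary. This is a worthwhile, inexpensive improvement to one reported figure and does not threaten the study's main aim.

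**What to change.** Replace the average in section 10 with the following:

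- Time runs from study consent to the date of confirmed diagnosis. The protocol does not say that this date is recorded, so add it to the case report form.
- Report the cumulative incidence of diagnosis at 6, 12 and 24 months over all enrolled patients. Censor undiagnosed patients at last contact or study end, and treat death as a competing event.
- State the number withdrawn. Section 8.4 removes their data, so they cannot be included as censored observations.
- Label any mean or median among solved patients as conditional on diagnosis.

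In the fixed-time illustration with 30 months as the longest time, the 24-month value is 0.33 × 0.8 = 26.4%. Closure at month 60 or 84 does not change what is being estimated.

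Consent is a choice of origin. Symptom onset or referral would answer a different question, so the origin must be named in any case. The cost is a few sentences, one date field and a little more analysis work. The resulting figure will look less flattering than a mean among solved patients.
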